**: Any of the following insulin monotherapies: mixed (rapid-acting or ultrarapid-acting insulin containing no more than 30% of volume), intermediate-acting, or long-acting soluble insulin preparations
- 8. The subject is not undergoing hemodialysis or peritoneal dialysis and has severe renal impairment (creatinine clearance [Ccr] <30 mL/min at the start of the screening period [Week -6]), or the subject is undergoing hemodialysis and has end-stage renal failure.
- 9. In the opinion of the investigator or sub-investigator, the initiation of hemodialysis or peritoneal dialysis within 12 weeks after initiation of the study drug is not expected. (in cases where the subject is not undergoing hemodialysis or peritoneal dialysis [patients with severe renal impairment])
- 10. The subject has been undergoing hemodialysis started from at least 6 months prior to informed consent and, in the opinion of the investigator or sub-investigator, the subject is clinically stable. (in cases where the subject is undergoing hemodialysis [patient with end-stage renal failure])
- 11. The subject is male or female and is aged 20 years or older at the time of informed consent.
- 12. A female subject of childbearing potential who is sexually active with a nonsterilized male partner agrees to routinely use adequate contraception from signing of informed consent until 1 month after the end of the study.
- 13. In the opinion of the investigator or sub-investigator, the subject is capable of understanding and complying with protocol requirements.
- 14. The subject signs and dates a written, informed consent form prior to the initiation of any study procedures.

Criteria for Exclusion:

1. The subject has clinically evident hepatic impairment (e.g., AST or ALT ≥ 2.5 times the upper limit of normal or total bilirubin of ≥ 2.0 mg/dL at the start of the screening period [Week -6] or at Week -2 of the screening period).
2. The subject has any serious cardiac diseases, cerebrovascular disorders, or serious pancreatic or hematological diseases (e.g., subjects who require inpatient treatment or had been hospitalized for treatment within 24 weeks prior to the start of the screening period).
3. The subject has severe ketosis, diabetic coma or pre coma, type 1 diabetes, severe infection, or severe external injury, or is immediately before or after surgery.
4. The subject has hemoglobinopathy (sickle cell disease, thalassemia, etc.).

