7.5 Criteria for Discontinuation or Withdrawal of a Subject

The primary reason for discontinuation or withdrawal of the subject from the study should be recorded in the case report form (eCRF) using the following categories. For screen failure subjects, refer to Section 9.1.25.

1. Pretreatment event (PTE) or AE

The subject has experienced a PTE or AE that requires early termination because continued participation imposes an unacceptable risk to the subject's health or the subject is unwilling to continue because of the PTE or AE.

Liver Function Test (LFT) Abnormalities

Study drug should be discontinued immediately with appropriate clinical follow-up (including repeat laboratory tests, until a subject's laboratory profile has returned to normal/baseline status [value at immediately after the informed consent for PTEs and at immediately before the initiation of the study drug for AEs], see Section 9.1.9), if the following circumstances occur at any time during study drug treatment:

- alanine aminotransferase (ALT) or aspartate aminotransferase (AST) $>8 \times$ upper limit of normal (ULN), or
- ALT or AST $>5 \times$ ULN and persists for more than 2 weeks, or
- ALT or AST $>3 \times$ ULN in conjunction with elevated total bilirubin $>2 \times$ ULN or international normalized ratio (INR) >1.5 , or
- ALT or AST $>3 \times$ ULN with appearance of fatigue, nausea, vomiting, right upper quadrant pain or tenderness, fever, rash and/or eosinophilia ($>5\%$).

• Renal Function Test Abnormalities

For subjects not on hemodialysis at the start of the screening period (Week -6) (patients with severe renal impairment), the study drug should be discontinued with

appropriate clinical follow-up until a subject's laboratory profile has returned to normal/baseline status for subjects not on hemodialysis at the start of the screening period (Week -6) (patients with severe renal impairment) if the subject shows worsening of renal function that may necessitate hemodialysis in Treatment Period I and is considered inappropriate to continue the study in the opinion of the investigator or sub-investigator, or if the subject shows rapid worsening of Ccr (e.g., reduction of 30% or more) on 2 consecutive post dose measurements, as compared with the value at the end of the screening period (Week 0), and is considered inappropriate to continue the study in the opinion of the investigator or sub-investigator.

- **Serious hypoglycemia**

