9.1.9 Procedures for Clinical Laboratory Samples

Clinical laboratory tests that will be performed in this study are shown in Table 9.a.

All samples will be collected in accordance with acceptable laboratory procedures. The maximum volume of blood at any single visit is approximately 27 mL, and the approximate total volume of blood for the study is 322 mL.

Table 9.a Clinical Laboratory Tests

Hematology	Serum Chemistry
Red blood cells	Alanine aminotransferase
Reticulocytes	Aspartate aminotransferase
White blood cells	γ -Glutamyl transferase
Hemoglobin	Alkaline phosphatase
Hematocrit	Total bilirubin
Platelets	Total protein
White blood cells with differential (neutrophils, lymphocytes, monocytes, eosinophils, basophils)	Albumin
Erythrocyte indices (MCV, MCH, MCHC)	Creatinine
	Amylase
	Lipase
	Blood urea nitrogen
	Uric acid
	Creatine kinase
	Lactate dehydrogenase
	Total cholesterol
	Triglyceride (fasting)
	Low-density lipoprotein (LDL) cholesterol (direct measurement)
	High-density lipoprotein (HDL) cholesterol
	high-sensitivity CRP
	Potassium
	Sodium
	Calcium
	Chloride
	Phosphate
	Ferrum
Other:	
Pregnancy test (serum or urine human chorionic gonadotropin [hCG]) (female subjects of childbearing potential)	

The central laboratory (Annex 1) will perform laboratory tests listed above except for the pregnancy test. Creatinine clearance (Ccr) will be calculated by the sponsor using the Cockcroft-Gault equation.

Cockcroft-Gault equation

Male: $Ccr = \{(140 - \text{age}) \times \text{weight (kg)}\} / \{72 \times \text{serum creatinine (mg/dL)}\}$

Female: $Ccr = 0.85 \times \{(140 - \text{age}) \times \text{weight (kg)}\} / \{72 \times \text{serum creatinine (mg/dL)}\}$

If subjects experience ALT or AST $>3 \times$ ULN, follow-up laboratory tests (at a minimum, serum alkaline phosphatase, ALT, AST, total bilirubin, GGT, and INR) should be performed within a maximum of 7 days and preferably within 48-72 hours after the abnormality was noted. (Refer to Section 7.5 and Section 10.2.3)

The results of laboratory tests will be returned to the investigator or sub-investigator, who is responsible for reviewing and filing these results. The investigator will also maintain a copy of the reference ranges including their amendment for the laboratory used.

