 - TEAEs that occur before the start of the study drug for Treatment Period II: The analysis will be performed based on the evaluation result entered in the CRF under “Pretreatment Event/Adverse Event (Period 1).”
 - TEAEs that occur after the start of SYR-472 25 mg tablet: The analysis will be performed based on the evaluation results entered in the CRFs under “Pretreatment Event/Adverse Event (Period 1)” and “Pretreatment Event/Adverse Event (Period 2 and thereafter).” If the

evaluation results differ between “Pretreatment Event/Adverse Event (Period 1)” and “Pretreatment Event/Adverse Event (Period 2 and thereafter),” the evaluation result of “Pretreatment Event/Adverse Event (Period 2 and thereafter)” will be preferentially used.

- Time of onset: In the analysis of TEAEs that occur before the start of the study drug for Treatment Period II, the time of onset will be calculated by defining the day of the start of the study drug administration as day 1. In the analysis of TEAEs that occur after the start of SYR-472 25 mg tablet, it will be calculated by defining the day of the start of SYR-472 25 mg tablet as day 1.
- Number of days from the immediate study drug administration: To be calculated by defining the day of the immediate study drug administration as Day 1. If the study drug administration and TEAE occur on the same day, the number of days from the immediate study drug administration will be defined as 1 day.
- Complications of hepatobiliary disorders: Concurrent medical conditions summarized as hepatobiliary disorders by SOC.
- MAV: An abbreviation for markedly abnormal value.
- Overall hypoglycemia: Hypoglycemia reported as “Yes” for hypoglycemic symptoms and asymptomatic hypoglycemia.
- Asymptomatic hypoglycemia: Hypoglycemia with an evaluable self-monitoring blood glucose value (i.e., non-missing and determined to be eligible based on “Handling Rules for Analysis Data”) and a measured concentration of ≤ 70 mg/dL but determined to be not accompanied by symptoms of hypoglycemia at the measurement of that blood glucose value. The presence or absence of asymptomatic hypoglycemia will be determined for each blood glucose value measured.

HANDLING OF TIME WINDOW

For each test, observation, and evaluation items, evaluable data (i.e., non-missing data and data determined to be eligible based on “Handling Rules for Analysis Data”) will be handled according to the following rules.

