Week 44	Study Day: 309	295 to 322		2 ~	~ 20
Week 48	Study Day: 337	323 to 350		2 ~	~ 20
Week 52	Study Day: 365	351 to 378		2 ~	~ 20
Week 54	Follow-up Day for SYR-472 25 mg Tablet: 21				21 to 28
At the End of Treatment Period I	Follow-up Day for Treatment Period I: 7	2 ~	~ 20	~ 1	
At the End of Treatment Period II	Follow-up Day for SYR-472 25 mg Tablet: 7			2 ~ *	~ 20

*: At the end of Treatment Period II, "Study Day for Treatment Period II" will be assumed to be "Study Day for SYR-472 25 mg tablet."

Vital signs, laboratory test, creatinine clearance, eGFR

Visit	Scheduled Study Day	Acceptable Window			
		Study Day	Follow-up Day for Treatment Period I	Study Day for Treatment Period II	Follow-up Day for SYR-472 25 mg Tablet
Week -6	Study Day: -42	-49 to -29			
Week -2	Study Day: -14	-28 to -8			
Week 0	Study Day: 1	-7 to 1			
Week 2	Study Day: 15	2 to 22	~ 20	~ 1	
Week 4	Study Day: 29	23 to 42	~ 20	~ 1	
Week 8	Study Day: 57	43 to 70	~ 20	~ 1	
Week 12	Study Day: 85	71 to 98	~ 20	~ 1	

Visit	Scheduled Study Day	Acceptable Window			
		Study Day	Follow-up Day for Treatment Period I	Study Day for Treatment Period II	Follow-up Day for SYR-472 25 mg Tablet
Week 16	Study Day: 113	99 to 126		2 ~	~ 20
Week 20	Study Day: 141	127 to 154		2 ~	~ 20
Week 24	Study Day: 169	155 to 182		2 ~	~ 20
Week 28	Study Day: 197	183 to 210		2 ~	~ 20
Week 32	Study Day: 225	211 to 238		2 ~	~ 20
Week 36	Study Day: 253	239 to 266		2 ~	~ 20
Week 40	Study Day: 281	267 to 294		2 ~	~ 20
Week 44	Study Day: 309	295 to 322		2 ~	~ 20
Week 48	Study Day: 337	323 to 350		2 ~	~ 20
Week 52	Study Day: 365	351 to 378		2 ~	~ 20
Week 54	Follow-up Day for SYR-472 25 mg Tablet: 21				21 to 28

12-lead ECG

Visit	Scheduled Study Day	Acceptable Window			
		Study Day	Follow-up Day for Treatment Period I	Study Day for Treatment Period II	Follow-up Day for SYR-472 25 mg Tablet
Week -6	Study Day: -42	-49 to -22			
Week 0	Study Day: 1	-21 to 1			
Week 4	Study Day: 29	2 to 56	~ 20	~ 1	
Week 12	Study Day: 85	57 to 98	~ 20	~ 1	
Week 24	Study Day: 169	99 to 210		2 ~	~ 20
Week 36	Study Day: 253	211 to 308		2 ~	~ 20
Week 52	Study Day: 365	309 to 378		2 ~	~ 20
Week 54	Follow-up Day for SYR-472 25 mg Tablet: 21				21 to 28

Plasma concentration of SYR-472Z

Visit	Scheduled Study Day	Acceptable Window			
		Study Day	Follow-up Day for Treatment Period I	Study Day for Treatment Period II	Follow-up Day for SYR-472 25 mg Tablet
Week 4	Study Day: 29	23 to 42	~ 20	~ 1	
Week 12	Study Day: 85	71 to 98	~ 20	~ 1	

OTHER HANDLING

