- Creatinine clearance (mL/min): To be calculated using the following Cockcroft-Gault equation (rounded off to the nearest integer in both cases).

Male: $([140 - \text{Age}] \times \text{Weight [kg]}) / (72 \times \text{Serum creatinine [mg/dL]})$

Female: $0.85 \times ([140 - \text{Age}] \times \text{Weight [kg]}) / (72 \times \text{Serum creatinine [mg/dL]})$

Creatinine clearance will be calculated when the variables to be used for calculation are all evaluable and measured on the same day. The age will be calculated from the test dates of variables to be used for calculation and the date of birth.
- eGFR (mL/min/1.73 m²): To be calculated using the following equation (rounded off to the nearest integer in both cases).

Male: $194 \times \text{Serum creatinine (mg/dL)}^{-1.094} \times \text{Age}^{-0.287}$

Female: $194 \times \text{Serum creatinine (mg/dL)}^{-1.094} \times \text{Age}^{-0.287} \times 0.739$

The age will be calculated from the test dates of variables to be used for calculation and the date of birth.
- Duration of disease (months): Period from the onset time of type 2 diabetes until the time of informed consent.
- Duration of study drug exposure for Treatment Period I: Date of the last administration of the study drug for Treatment Period I – Date of the start of the study drug administration for Treatment Period I + 1
- Compliance with study drug for Treatment Period I: Number of study drug administrations for Treatment Period I / (Smallest integer of \geq [(Date of the last administration of the study drug for Treatment Period I – Date of the start of the study drug administration for Treatment Period I + 7) / 7]) $\times 100$ (rounded off to the first decimal place)
- Duration of exposure to SYR-472 25 mg tablet: Date of the last administration of SYR-472 25 mg tablet – Date of the start of SYR-472 25 mg tablet + 1
- Compliance with SYR-472 25 mg tablet: Number of administrations of SYR-472 25 mg tablet / (Smallest integer of \geq [(Date of the last administration of SYR-472 25 mg tablet – Date of the start of SYR-472 25 mg tablet + 7) / 7]) $\times 100$ (rounded off to the first decimal place)

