2.4.2 Handling of Dropouts or Missing Data

Missing test results and ineligible data according to the “Handling Rules for Analysis Data” or the SAP will be excluded from statistical analyses and estimations.

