3.3 Clinical Laboratory Evaluations and Other Safety Endpoints

3.3.1 Clinical Laboratory Evaluations

3.3.1.1 Hematology and Serum Chemistry

Analysis set:	Safety analysis set		
Analysis variables:	Hematology		
	Red blood cells	Reticulocytes	White blood cells
	Hemoglobin	Hematocrit	Platelets
	Neutrophils	Lymphocytes	Monocytes
	Eosinophils	Basophils	MCV
	MCH	MCHC	
	Serum chemistry		
	ALT	AST	
	γ-GTP	ALP	
	Total bilirubin	Total protein	
	Albumin	Creatinine	
	Amylase	Lipase	
	Blood urea nitrogen	Uric acid	
	Creatine kinase	LDH	
	Total cholesterol	Triglyceride	
	LDL cholesterol	HDL cholesterol	
	High-sensitivity CRP	K	
	Na	Ca	
	Cl	P	
	Fe	Creatinine clearance	
Categories:	Adjudication results based on the normal reference ranges [Low, Normal, High]		
Visits:	Weeks -6, -2, 0, 2, 4, 8, 12, 16, 20, 24, 28, 32, 36, 40, 44, 48, 52, and		

Analysis methodology: The following analysis will be performed for the above analysis variables except for high-sensitivity CRP and creatinine clearance by treatment group. The following analyses of (1) to (2) will be performed for high-sensitivity CRP and creatinine clearance by treatment group.

When the analysis of MAV is performed, if both “upper” and “lower” criteria in the MAV Criteria are applicable to the same test item, the analysis will be performed for each criterion separately. See Appendix 2 of this SAP for the definitions of test items subject to this analysis and the MAV Criteria.

- (1) Summary statistics for each visit and summary statistics for change from Week 0 at each visit after Treatment Period I
- (2) Case plots
- (3) Shift tables showing adjudication results based on normal reference range at Week 0 and each visit after Treatment Period I
- (4) Frequency distributions for MAV before the start of the study drug administration for Treatment Period II and after the start of SYR-472 25 mg tablet

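### SAP 3.3.1.1 pools dialysed and non-dialysed subjects in its creatinine clearance summaries; the hemodialysis split the SAP already uses elsewhere would serve better

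*SAP*

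**What the plan says.** SAP 3.3.1.1 works in the safety analysis set. For two of its laboratory variables it prescribes a reduced set of outputs: "The following analyses of (1) to (2) will be performed for high-sensitivity CRP and creatinine clearance by treatment group". Analysis (1) is summary statistics by visit with change from Week 0, and (2) is case plots. The shift tables (3) and markedly abnormal value counts (4) do not apply to Ccr. The section has no stratum line.

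On derivation, Protocol 9.1.9 says "Creatinine clearance (Ccr) will be calculated by the sponsor using the Cockcroft-Gault equation", with no restriction by dialysis status. SAP Other Handling adds "Creatinine clearance will be calculated when the variables to be used for calculation are all evaluable and measured on the same day". The SAP's time-window section speaks of "evaluable data (i.e., non-missing data and data determined to be eligible based on" the Handling Rules for Analysis Data. SAP 2.4.2 says that data ineligible under those rules "or the SAP will be excluded from statistical analyses and estimations". The Handling Rules are not among the supplied documents.

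Inclusion criterion 8 admits two kinds of subject, and Ccr defines only one of them: "Ccr] <30 mL/min at the start of the screening period [Week -6]), or the subject is undergoing hemodialysis and has end-stage renal failure". The renal withdrawal rule in Protocol 7.5 is confined in the same way, opening with "For subjects not on hemodialysis at the start of the screening period (Week -6) (patients with severe renal impairment".

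Protocol 9.1.19 has the start of hemodialysis and its date recorded, through the end of the study, for subjects not on it at entry.

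**The concern.** A by-arm mean of Ccr over the whole safety set mixes subjects in whom the protocol uses Ccr with subjects in whom it does not. If Ccr in the dialysed subjects does not follow the non-dialysed change, the table understates any change in the subjects whose kidney function can still be followed this way. A subject who starts dialysis during the trial may also keep contributing Ccr values to the mean. This is a trial in severe renal impairment and end-stage renal failure, so a reader of the safety report will look at this table for the renal course.

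**Working it through.** There is no figure in the plan to reproduce. The documents state neither the dialysed share nor an expected Ccr change. The check is a reading of the SAP followed by an illustration.

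**1. Where hemodialysis appears in the SAP.** It is a baseline descriptor in 1.2.1. It is a stratum in 2.4.8 (HbA1c change), 2.5 (plasma concentration) and 3.1.3 (treatment-emergent adverse events, TEAEs). It does not appear in 3.3.1.1.

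**2. Is there another renal-function estimate?** The visit-window table headed "Vital signs, laboratory test, creatinine clearance, eGFR" runs to Week 54, but eGFR is used only at Week 0 (1.2.1, 2.4.8, 3.1.3). In the supplied text Ccr is therefore the only renal-function estimate tabulated after Week 0.

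**3. Dilution.** Let h be the dialysed share of subjects contributing Ccr, dN the mean change in non-dialysed subjects and dD the mean change in dialysed subjects.

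Pooled change = (1 - h) × dN + h × dD

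With r = dD/dN, pooled change / dN = (1 - h) + h × r. Both h and r are assumptions:

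| h | r = 0 (dialysed flat) | r = 0.5 | r = 1 (equal change) |
|---|---|---|---|
| 0.2 | 0.80 | 0.90 | 1.00 |
| 0.3 | 0.70 | 0.85 | 1.00 |
| 0.5 | 0.50 | 0.75 | 1.00 |
| 0.7 | 0.30 | 0.65 | 1.00 |
| 0.8 | 0.20 | 0.60 | 1.00 |

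The factor falls further if dialysed Ccr moves the opposite way, and exceeds 1 if it moves more than the non-dialysed Ccr. For a between-group difference, if h and dD are the same in both arms, the pooled difference is (1 - h) times the non-dialysed difference.

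**4. Would the split leave usable numbers?** With the planned 53 randomised per group, the non-dialysed stratum holds 53 × (1 - h): about 37 at h = 0.3, 26 to 27 at h = 0.5 and 16 at h = 0.7. That is enough for descriptive summaries.

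**5. Values after dialysis starts.** Cockcroft-Gault has serum creatinine in the denominator. If creatinine falls once dialysis begins (assumption), the formula returns a higher Ccr and the subject looks improved. Inclusion criterion 9 covers expected dialysis only in the first 12 of 52 weeks. The supplied text does not say how such values are handled.

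**6. Counting dialysis starts.** No table in the supplied SAP uses the data collected under Protocol 9.1.19. The nearest output, renal impairment TEAEs (SAP 3.1.2, item 18), counts adverse event terms. Protocol 10.1.3 records worsening of a degenerative concurrent condition only when it exceeds what would be expected, so a dialysis start through expected progression might not appear there.

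**The case against.** The strongest reply is that the SAP does what it was asked to do. Protocol 13.1.4 calls for laboratory summaries by treatment group and time point plus case plots, and 3.3.1.1 delivers them. A reader might infer that the SAP contradicts the protocol. It does not: no passage promises a dialysis split of any laboratory variable, and dialysis introduction is not an endpoint. This objection stands, and makes the point an improvement rather than a correction of an inconsistency.

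Second, the Handling Rules are unseen and might remove some values. The supplied text is also unclear on its own terms: Protocol 9.1.5 uses dry weight for dialysed subjects, and whether that counts as measured on the same day as creatinine is not stated. How many dialysed subjects will contribute Ccr is therefore unknown. This also stands, and is why the statement is limited to the supplied text.

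Third, a reader might infer that renal safety goes unexamined. That is not supported. There are Ccr case plots; creatinine and urea summaries and shift tables, though also pooled; renal impairment TEAEs; and, in 3.1.3, all and drug-related TEAEs by hemodialysis and by eGFR stratum. None of these gives a summary of renal function by dialysis status, so the gap is narrowed but not closed.

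Fourth, the lack of a table of dialysis starts need not be an oversight. Transfusions and hospitalisations of a week or more are also recorded without their own SAP table, and such items may serve data handling. For that reason the count is only an option here. Most starts would be expected in Treatment Period II, when both groups take SYR-472 and no placebo comparison exists.

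**Conclusion.** The point holds as a minor, descriptive improvement. In the supplied text, the only post-baseline renal-function summary pools subjects in whom the protocol uses Ccr with subjects in whom it does not, while the SAP already has the stratum that would separate them.

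The size cannot be fixed from the documents. Under flat dialysed Ccr and h between 0.2 and 0.8, both assumed, the pooled change is 80% to 20% of the non-dialysed change; with equal change there is no dilution. A reader might want to turn this into a loss in mL/min or compare it with the 30% fall given as an example in Protocol 7.5. Neither is supported: no expected change is stated, and the 7.5 example concerns consecutive values in one subject with investigator judgement, not a group mean.

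Nor does pooling bias the randomised comparison; it describes the whole safety set, as labelled. The primary HbA1c analysis and the individual rule in 7.5 are unaffected.

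**What to change.** In SAP 3.3.1.1:

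- Present the Ccr summaries, change from Week 0 and case plots by baseline hemodialysis status within treatment group, and treat the non-dialysed stratum as the renal-function summary. Do the same for serum creatinine and urea, which are pooled in the same way.
- State the reference time for that status. The SAP's hemodialysis entries give no week; Protocol 7.5 uses Week -6.
- In the non-dialysed stratum, flag or separate values obtained after dialysis introduction, or cite the Handling Rule that already covers them.

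Optional: one table of the number and percentage of initially non-dialysed subjects in whom hemodialysis was introduced, by treatment group, over the two intervals already used for TEAEs. For the interval from the first 25 mg tablet, the denominator is the initially non-dialysed subjects who took that tablet. In the SYR-472 group the two intervals overlap, which a footnote should say.

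The cost is SAP wording, a stratum already in use, one flag and, if wanted, one small table. Hemodialysis status and the introduction date are in the eCRF and creatinine comes from the central laboratory, so nothing new is collected and no test is added.
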